8.2.8 Vital signs

Blood pressure, heart rate and oxygen saturation will be measured after the patient has been at rest for at least 5 minutes.

Blood pressure (systolic and diastolic) will be measured by means of a standard manual or an automatic blood pressure measuring device (cuff method) in sitting or supine position. Nevertheless, the same method and body posture should be used during the entire study period (the type of device has to be recorded into the CRF). The same upper arm will be used for each

EudraCT: 2021-001633-40	Version 1.7 15.01.2025	ESRA
-------------------------	---------------------------	------

measurement of blood pressure, preferably the left arm. Heart rate and SpO₂ will be measured by pulse oximetry.

8.2.9 Electrocardiography

A 12-lead electrocardiogram (ECG) will be performed. For deriving the 12-lead ECGs the patients should always be in supine position. The 12-lead ECGs should be derived after a resting period of at least 10 minutes. The investigator will review the ECGs for potential AEs.

A continuous 12-lead ECG monitoring will be applied during right heart catheterization.

8.2.10 Clinical laboratory investigations

Clinical laboratory investigations will comprise:

Hematology	Leucocytes, erythrocytes, hemoglobin, hematocrit, platelets
Substrates	Bilirubin, cholesterol, triglycerides, creatinine, uric acid, urea, total protein, glucose
Electrolytes	Sodium, potassium, calcium, chloride
Enzymes	SGOT/ASAT, SGPT/ALAT, Gamma-GT, AP, LDH, CK
Others	INR, PTT, β-HCG test or urine dipstick for WOCBP
Biomarkers	CRP, NT-proBNP

All laboratory assessments will be determined locally on-site. Any leftover biomaterials will be destroyed in line with local regulations.

8.3 Study Phases and Visits

8.3.1 Screening Phase

Patients who sign the informed consent form to participate in the medical trial will undergo the screening examinations: medical history, demographics, checking of in- and exclusion criteria, physical and weight examination, vital signs (blood pressure, heart rate, SpO₂), lung function test (body plethysmography and diffusion capacity), blood gas analysis (BGA), echocardiography at rest, right heart catheterization with continuous 12-lead ECG at rest, clinical laboratory, including pregnancy test (only WOCBP), survey of concomitant medication and diseases and recording of adverse events. Measurements/assessments taken during screening visit will be recorded as baseline values for study assessment of endpoints unless described otherwise.

The right heart catheterization should not be older than 1 month at screening or not older than 6 months if the patient had no signs of clinical changes defined as change of 6MWD >10%, WHO-FC change or >30% change in NT-proBNP. RHC must have been measured in the participating

EudraCT: 2021-001633-40	Version 1.7 15.01.2025	ESRA
-------------------------	---------------------------	------

center under standardized conditions. Patients without recent RHC fulfilling the above-mentioned criteria, will receive a RHC at screening, be before the beginning of the intervention. Baseline will be within 28 days after screening.

If, due to organisational reasons, echocardiography cannot be performed at Baseline, it can be performed during Screening period and it can be used as baseline value. Echocardiography cannot be performed after baseline.

8.3.2 Visit 1 Baseline / Randomization - Day 1

Baseline visit may be performed according to the hospital's routine practice as in-hospital stay.

The baseline visit includes the following assessments/measurements: physical examination, SSc characteristics including the WHO-FC, vital signs (blood pressure, heart rate, SpO₂), weight, 12-lead ECG, clinical laboratory (including pregnancy test only for WOCBP), echocardiography, 6MWD including Borg Dyspnea Score, QoL questionnaire (SF-36), concomitant medications, diseases/clinical symptoms and adverse events. If it is not possible to perform all requested assessments for visit 1 at one day, it is allowed to split the visit and to conduct the required measurements at two consecutive days. If screening and baseline are conducted during the same hospital stay following assessments will only be performed once, otherwise at screening and baseline: 12-lead ECG, physical examination, concomitant medication, lung function testing, DLCO, blood gas analysis pregnancy test (WOCBP only), hematology, chemistry and NT-proBNP.

If, due to organisational reasons, echocardiography cannot be performed at Baseline, it can be performed during Screening period and it can be used as baseline value. Echocardiography cannot be performed after baseline.

Patient's eligibility to participate in the trial will be confirmed. Subsequently, patients will be randomized. After the explanation of intake and titration, study medication (riociguat (MK-4836) or placebo) and the patient diary will be handed out to patients.

8.3.3 Visit 1.1- Visit 1.4 - Titration phase (week 2, 4, 6, 8 ± 2 days)

Double-blind riociguat (MK-4836) vs. placebo treatment will be initiated and individually adjusted according to systolic blood pressure and tolerability. During the titration phase, each patient will be asked to measure their peripheral systolic blood pressure and the heart rate at home three times

EudraCT: 2021-001633-40	Version 1.7 15.01.2025	ESRA
-------------------------	---------------------------	------

per day and document the values in the patient diary. The results will be examined by the investigator during each visit/phone call-visit. The patient will be handed out a diary to document the blood-pressure at study start (see Appendices). Provided that the systolic blood pressure is \geq 95 mmHg measured at trough before intake of each dose and the patient has no signs or symptoms of hypotension, the dose of study medication will be titrated by +0.5 mg tid every 2 weeks until the maximal tolerated dosage with a maximal permitted dosage of 2.5 mg tid under consideration of the titration algorithm (= individual dose titration scheme). After the titration period, blood pressure should be measured upon signs or symptoms of hypotension. WOCBP have to perform pregnancy tests at home in week 4 (visit 1.2) and 8 (visit 1.4). Adverse events and concomitant medication will be recorded.

To ensure blinding, subjects allocated to the placebo group undergo a sham titration from Visit 1 onwards that follows the rules of the individual dose titration scheme. Independently of the investigator's decision to increase, maintain or decrease the dose of the study medication blinded placebo medication will be allocated.

8.3.4 Visit 2 - 12 weeks assessment (\pm 7 days)

During the main study phase (weeks 9-24), all subjects are to remain on their optimal dose of riociguat (MK-4836) or placebo. Dose reductions for safety reasons are allowed, but a subsequent re-increase during the main study phase is not possible. In case of dose delays, patients may be further titrated according to tolerability up to week 12. Clinical evaluations and phone visits are to be scheduled according to the physician's estimation and patient safety.

Visit 2 procedures/assessments include the following: WHO-FC, vital signs, physical examination, laboratory, 6MWD and Borg dyspnea score will be assessed and concomitant medications, weight, ECG, drug compliance, adverse events and diseases/clinical symptoms will be recorded. The patient diary will be examined. Unused study drug will be collected and medication for the remaining 12 weeks at maintenance dose will be dispensed.

8.3.5 Phone visit 2.1 and phone visit 2.2 – WOCBP only (week 16 and 20 \pm 2 days)

WOCBP have to perform pregnancy tests at home in week 16 (visit 2.1) and 20 (visit 2.2) and the results will be assessed by phone.

EudraCT: 2021-001633-40	Version 1.7 15.01.2025	ESRA
-------------------------	---------------------------	------

8.3.6 Visit 3 – 24 weeks assessment ± 14 days (termination of double-blind study)

After 24 weeks ± 14 days, patients will be assessed by clinical evaluation.

Visit 3 procedures/assessments include the following: physical examination, WHO-FC, vital signs, laboratory (including pregnancy test only for WOCBP), weight, ECG, lung function test (plethysmography and diffusion capacity test), BGA, QoL (SF-36 questionnaire), 6MWD and Borg dyspnea score, echocardiogram, right heart catheterization, drug compliance, concomitant medications, adverse events and diseases/clinical symptoms will be recorded. Unused study drug will be collected and the patient diary examined.

8.3.7 Visit 4 - Safety follow-up 30 days after last IMP intake

Patients will be contacted via phone 30 days after their last intake of study drug (±14 days). The assessment will serve to monitor adverse events, concomitant medication, safety and tolerability, and in case of WOCBP pregnancy test results. Clinical follow-up of all SAEs will be performed until they have been resolved, if possible.

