Riociguat (MK-4836) dose will be individually adjusted in accordance with the in-label titration regimen. Dose adjustment will be performed every two weeks by phone taking the systemic blood pressure of the patient, the subjects and physicians' subjective estimation and occurrence of adverse reactions into account. At week 8 the maintenance dose will be established and furtherly continued for the rest of the study.

Interim Visit / Visit 2 (week 12)

At the interim visit in week 12 assessments from screening /baseline will be repeated (except RHC and medical history) as described in Section “8.1 Overview of visits and assessments”. Unused study drug will be collected and medication for the remaining 12 weeks at maintenance dose will be supplied.

Termination visit / Visit 3 (week 24)

At this visit in week 24 assessments will be conducted as described in Section “8.1 Overview of visits and assessments”.

Follow-up / Visit 4 (30 days after last study drug intake)

Phone call 30±14 days after last study drug intake to assess adverse events and record a final pregnancy test (WOCBP only).

[figure not shown]
Excluded medication:

Pirfenidon; nintedanib, prednisolone >10 mg/day, PAH specific treatment

EudraCT: 2021-001633-40	Version 1.7 15.01.2025	ESRA
-------------------------	---------------------------	------

Pre-treatment period:	N/A
Duration of observation	Up to 28 days screening period, 24 weeks double-blind, controlled study phase, + 30 days follow-up
Follow-up period	30 days after week 24 visit each patient performs a follow-up visit via phone. Clinical follow-up of all SAEs until they have been resolved or improved if possible.
Clinic visits	Double-blind: Screening visit, baseline visit, week 12 and week 24 Additional titration visits every two weeks via phone in the double-blind study phase (week 2, 4, 6, 8), and phone follow-up 30 days after last study drug intake.
Dosing regimen	Individual adjustment during the 8 weeks titration period according to the in-label titration regimen
Route of administration	Oral riociguat (MK-4836) or respective placebo
Endpoints	All endpoints will be compared riociguat (MK-4836) vs. placebo:
Primary	Pulmonary vascular resistance, change from baseline to 24 weeks

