Medical examinations comprise of medical history, physical examination, electrocardiogram (ECG), blood gas analyses, lung function tests, DLCO, WHO-FC, 6MWD, quality of life questionnaires, laboratory testing (including NT-proBNP), echocardiography at rest, and right heart catheterization (RHC) according to clinical practice. If patients fulfil the inclusion criteria they will be invited to join the study. The prospective period of data collection will comprise of a 24-week study period and a follow-up phase of about 30 ± 14 days.

After the pre-treatment phase, eligible subjects will be randomized at Visit 1 in a 1:1 ratio to the following 2 treatment groups

- Riociguat (MK-4836) 1.0-2.5 mg group (titration between 1.0 mg and 2.5 mg tid based on an individual dose titration scheme)
- placebo group (placebo tid)

5 Trial Duration and Schedule

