5.1 Study Phases

- Screening Phase: up to 28 days before treatment start
- Treatment phase: 24 weeks \pm 14 days including 8 weeks titration phase and 16 weeks continuation phase.
- Safety Follow-up: patient's well-being will be monitored by phone after 30 ± 14 days after last intake of study drug.

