6. Women without childbearing potential defined as postmenopausal women with amenorrhea for at least 12 consecutive months and a serum FSH level within the laboratory's reference range for postmenopausal females, women with bilateral tubal ligation, women with bilateral ovariectomy, and women with hysterectomy can be included in the study.
7. Women of childbearing potential can only be included in the study if all of the following applies (listed below):
 - a. Negative serum pregnancy test at screening and at study start (visit 1).
 - b. Agreement to undertake monthly urine pregnancy tests during the study and up to at least 30 days after study treatment discontinuation. These tests should be performed by the patient at home.
 - c. Agreement to use a highly effective contraception method from screening until at least 30 days after last dose of study medication.

EudraCT: 2021-001633-40	Version 1.7 15.01.2025	ESRA
-------------------------	---------------------------	------

Option 1 or One method from this list	Option 2	or Option 3	or Option 4
Tubal sterilization (occlusion or ligation of tubes at least 6 weeks prior to Screening)	Oral*, Implantable*, Transdermal*, or Injectable* hormonal contraceptives Intrauterine Devices	Sterilization of the male partner with documented post-vasectomy confirmation of the absence of sperm in the ejaculate PLUS one method from this list Oral*, Implantable*, Transdermal*, or Injectable* hormonal contraceptives Intrauterine devices Diaphragm, female condom cervical cap, partner's use of a condom	True abstinence from intercourse with a male partner only when this is in line with the preferred lifestyle of the subject.

* If a hormonal contraceptive is chosen from this group, it must have been taken for at least 28 days prior to study start (visit 1).

8. Patients who are able to understand and follow instructions and who are able to participate in the study for the entire period.
9. Patients must have given their written informed consent to participate in the study after having received adequate previous information and prior to any study-specific procedures.

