8.1 Overview of visits and assessments

Assessments	Double-blind						
	Screening -28 days	Visit 1 Baseline Day 1	V 1.1-1.4 Phone Visits Titration Week 2, 4, 6 and 8 ±2 days	Visit 2 Interim visit Week 12 ±7 days	V 2.1-2.2 Phone Visits Only WOCBP Week 16 and 20 ±2 days	Visit 3 Terminatio n visit Week 24 ±14 days	Visit 4 Safety FU 30 days after last IMP intake ±14 days
Informed Consent	1	-	-	-	-	-	-
Inclusion / exclusion criteria	1	1	-	-	-	-	-
Patient diary(handing out / compliance check)	-	1	-	1	-	1	-
Prior and concomitant medication	1	1°	4	1	2	1	1
Demography, height and medical history	1	-	-	-	-	-	-
PAH classification, etiology, diagnosis date	1	-	-	-	-	-	-
WHO-FC	-	1	-	1	-	1	-
Vital signs, incl. heart rate, SpO ₂ (%)	1	1	-	1	-	1	-
6MWD, Borg Dyspnea Score	-	1	-	1	-	1	-
Weight	1	1°	-	1	-	1	-
ECG	1	1°	-	1	-	1	-
Blood gas analysis	1	1°	-	-	-	1	-
Lung function testing (Plethysmography)	1	1°	-	-	-	1	-
Diffusing capacity of the lung	1	1°	-	-	-	1	-
Right heart catheter	1*	-	-	-	-	1	-
Physical examination	1	1°	-	1	-	1	-
Laboratory Hematology, Chemistry, Hemostaseology, NT-proBNP	1	1°	-	1	-	1	-
Pregnancy test (only WOCBP)	1	1°¶	2 ⁺ (week 4 and 8)	1	2 ⁺ (week 16 and 20)	1	1 ⁺
Echocardiography	-#	1 [#]	-	-	-	1	-
Quality of life (SF-36)	-	1	-	-	-	1	-
Adverse Events	1	1	4	1	2	1	1
Systolic blood pressure and dose adjustment	-	-	4	-	-	-	-
Drug dispensed	-	1	-	1	-	-	-
Drug collected	-	-	-	1	-	1	-
Drug compliance	-	-	-	1	-	1	-
Phone visits	-	-	4	-	2	-	1

* RHC at screening will only be performed in patients who have not had a RHC within the preceding 1 month at screening. A preceding RHC from the last 6 months can be used if the patient had no signs of clinical changes defined as change of 6MWD >10%, WHO-FC change or >30% change in NT-proBNP. RHC must have been measured in the participating center under standardized conditions.

† Pregnancy test at home.

‡ Handing out pregnancy tests for home use

§ Will not be performed if already performed at Screening AND if Screening and Baseline are conducted during same hospital stay.

Optional during the SARS-CoV2-pandemic.

¶ If, due to organisational reasons, echocardiography cannot be performed at Baseline, it can be performed during Screening period and it can be used as baseline value. Echocardiography cannot be performed after baseline.

EudraCT: 2021-001633-40	Version 1.7 15.01.2025	ESRA
-------------------------	---------------------------	------

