- Home pregnancy test: women will perform a home pregnancy test in the morning before the telephone visits at weeks 4, 8, 16, 20 and for telephone follow-up 30 days after the end of the study. Please record the result (negative or positive) as well as date and time of the test in the patient diary (Table 2 of the diary). A single table is provided for all telephone visits. Pregnancy tests will be provided to you in advance by your study team.

Please note:

If possible, always take the study medication at the same time of day. If you forget to take it at one point in time, do not take a double dose at the next point in time. The bottles of tablets you will receive will last until your next visit to the hospital.

Please take the medicine three times a day.

Center No.:

Patient No.:

Month/Year:

Diary - Table 1: Tablet intake and vital parameters

Day	Dose and time of tablet intake							
	Vital parameters (VP)=blood pressure and pulse (VP) from week 0-8 only.		Vital parameters (VP)=blood pressure and pulse (VP) from week 0-8 only.		Vital parameters (VP)=blood pressure and pulse (VP) from week 0-8 only.			
	morning hh:mm blood pressure/pulse	noon hh:mm blood pressure/pulse	evening hh:mm blood pressure/pulse	comments				
1	____ mg ____/____mmHg	____:____ ____/____min	____ mg ____/____mmHg	____:____ ____/____min	____ mg ____/____mmHg	____:____ ____/____min		
2	____ mg ____/____mmHg	____:____ ____/____min	____ mg ____/____mmHg	____:____ ____/____min	____ mg ____/____mmHg	____:____ ____/____min		
3	____ mg ____/____mmHg	____:____ ____/____min	____ mg ____/____mmHg	____:____ ____/____min	____ mg ____/____mmHg	____:____ ____/____min		
4	____ mg ____/____mmHg	____:____ ____/____min	____ mg ____/____mmHg	____:____ ____/____min	____ mg ____/____mmHg	____:____ ____/____min		
5	____ mg ____/____mmHg	____:____ ____/____min	____ mg ____/____mmHg	____:____ ____/____min	____ mg ____/____mmHg	____:____ ____/____min		
6	____ mg ____/____mmHg	____:____ ____/____min	____ mg ____/____mmHg	____:____ ____/____min	____ mg ____/____mmHg	____:____ ____/____min		
7	____ mg ____/____mmHg	____:____ ____/____min	____ mg ____/____mmHg	____:____ ____/____min	____ mg ____/____mmHg	____:____ ____/____min		
8	____ mg ____/____mmHg	____:____ ____/____min	____ mg ____/____mmHg	____:____ ____/____min	____ mg ____/____mmHg	____:____ ____/____min		
9	____ mg ____/____mmHg	____:____ ____/____min	____ mg ____/____mmHg	____:____ ____/____min	____ mg ____/____mmHg	____:____ ____/____min		

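### The ±14-day window at Visit 4 lets the last scheduled pregnancy test fall on days 16–29 after the last dose, short of the 30-day minimum in inclusion criterion 7b

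*Protocol*

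**What the plan says.** **The minimum.** Protocol section 6.3, criterion 7b, makes entry for women of childbearing potential conditional on this: "Agreement to undertake monthly urine pregnancy tests during the study and up to at least 30 days after study treatment discontinuation". Criterion 7c sets a parallel minimum of at least 30 days after the last dose for highly effective contraception.

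**The schedule.** Section 8.3.7 gives the timing of Visit 4: "Patients will be contacted via phone 30 days after their last intake of study drug (±14 days". It lists pregnancy test results among the items collected. The synopsis, under Follow-up / Visit 4, shows that this is the last test and that it shares the call's window: "Phone call 30±14 days after last study drug intake to assess adverse events and record a final pregnancy test (WOCBP only". The Visit 4 column of the table in section 8.1 has one home pregnancy test under the heading "30 days after last IMP intake ±14 days", and the SAP visit schedule (section 4) repeats that column. The same tolerance appears in section 4 ("a follow-up phase of about 30 ± 14 days"), in section 5.1 ("will be monitored by phone after 30 ± 14 days after last intake of study drug"), and in sections 5.2 and 8.5.

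**The patient's instructions.** The diary in section 18 times the women's home testing as follows: "in the morning before the telephone visits at weeks 4, 8, 16, 20 and for telephone follow-up 30 days after the end of the study".

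**A second starting point.** The Follow-up period row of the synopsis counts from a different event: "30 days after week 24 visit each patient performs a follow-up visit via phone".

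**The concern.** Criterion 7b states a minimum with no minus tolerance, while the visit that delivers the last test has a tolerance of two weeks in both directions. A site can phone early, record the test, close follow-up and be fully in window, although testing has stopped sooner than the woman was required to agree to. Because the call is in window, it would not show up as a visit-window deviation, so nothing would prompt a later test.

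What is at stake is safety coverage after exposure to the drug. The protocol treats pregnancy as important: a confirmed positive serum test is a reason to stop treatment (section 6.5.1), and pregnancy must be reported to the manufacturer within one working day of notice (section 9.4). The other home tests tied to phone visits, at weeks 4, 8, 16 and 20, have windows of ±2 days (section 8.1). The widest window is on the test to which a stated minimum applies.

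**Working it through.** **Inputs**

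- Minimum duration of testing after treatment stops: 30 days (section 6.3, criterion 7b).
- Visit 4 target: day 30 after last intake (section 8.3.7).
- Visit 4 tolerance: ±14 days (section 8.3.7; also the synopsis and section 8.1).
- Position of the Visit 4 test: final (synopsis, Follow-up / Visit 4).

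**Step 1. The window as written**

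- Earliest day: 30 − 14 = 16.
- Latest day: 30 + 14 = 44.
- Permitted days: 44 − 16 + 1 = 29.

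**Step 2. Comparison with the minimum**

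- Days below 30: 16 to 29, which is 29 − 16 + 1 = 14 days.
- Days at or above 30: 30 to 44, which is 44 − 30 + 1 = 15 days.
- Share of permitted days below the minimum: 14/29 = 48.3%.
- Largest shortfall: 30 − 16 = 14 days.

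The 48.3% describes the window only. The documents do not say how calls are spread across it, and with day 30 as the target there is no reason to assume an even spread.

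**Step 3. Does other text close the gap?**

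- *Schedule (section 8.1).* After Visit 3 the only pregnancy test is the home test at Visit 4.
- *Section 8.5.* The trial ends with the last patient's follow-up call, under the same ±14-day window.
- *Section 8.6.* The six further months of follow-up offered to patients mention no pregnancy test.
- *Diary.* It names day 30 without a tolerance, but it links the test to the telephone follow-up and counts from the end of the study, not from the last tablet.
- *Repeat testing.* No text asks for a repeat after an early call, or for a test on or after day 30 whatever the call date.

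**Step 4. Who is covered**

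The gap applies to women who complete treatment and to those who leave the study when treatment stops. Women who stop the drug early but remain in the visit schedule can have further tests at later visits, so they are outside this point.

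**Step 5. The window after the change**

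With −0/+14 the permitted days are 30 to 44, or 15 days, and none is below the minimum.

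**The case against.** The strongest reply is that the two rules do not contradict each other. Criterion 7b records what the woman agrees to do, and section 8.3.7 tells the site when to phone. Any call on days 30 to 44 satisfies both, the target day is 30 wherever one is given, and an early call does not cancel her agreement. That much is right: the window permits the shortfall and does not force it. It does not remove the problem, because a schedule should deliver the testing that the entry criterion requires, and here a compliant call can end it early.

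Other safeguards also remain. Contraception is required to at least 30 days after the last dose, and section 9.4 sets no cut-off at Visit 4 for reporting a pregnancy that comes to notice later. These reduce the consequence, but neither replaces a test.

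The differing starting point in the synopsis is a side issue. For completers, whose remaining drug is collected at the week 24 visit, the two starting points should nearly coincide.

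Finally, the SAP reports that the trial has already stopped at 35 patients, so a correction now protects few participants or none. This stands, and it limits the practical value to any follow-up still open and to a consistent document. A lighter remedy, one sentence asking for a repeat test after an early call, would also close the gap while keeping the full call window.

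**Conclusion.** The point holds. For women of childbearing potential who complete treatment or leave the study when it stops, a Visit 4 call within its window can end scheduled pregnancy testing as early as day 16. That is up to 14 days below the protocol's own minimum. Of the 29 permitted days, 14 are too early.

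This rests on reading criterion 7b as the intended duration of testing and on the Visit 4 test being the last one scheduled, which is how the synopsis describes it. The number of women of childbearing potential is not given, so the number at risk of an early final test cannot be estimated. Efficacy, power and type I error are untouched. It is a minor inconsistency in the safety schedule, worth correcting because the correction is cheap.

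**What to change.** - For women of childbearing potential, set the Visit 4 window to 30 days −0/+14 after last study drug intake. Make the change wherever the window appears: the synopsis, protocol sections 4, 5.1, 5.2, 8.1, 8.3.7 and 8.5, and the SAP visit schedule.
- Add a diary line telling women to do the final home test no earlier than 30 days after the last tablet.
- Change the Follow-up period row of the synopsis so that it also counts from last intake.

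The cost is the same small edit in about eight places, one diary line, and a call window of 15 days instead of 29 for these women. No visit is added, and the latest permitted day stays at 44.
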